#### 2.4.3 Prior, concomitant and post therapies

Prior and concomitant medications will be summarized in separate tables for the SAF. Medications will be coded using the WHO Drug Dictionary (WHODD). The latest version of which (at the time of the data cut-off) will be used for the reporting activity.

Medications will be classified as prior, or concomitant as follows:

- Prior medications are defined as drugs taken (including MS medication) and stopped prior to first study treatment administration.
- Concomitant medications are defined as drugs taken at least once between first and last study treatment administration (including those which were started prior to first study treatment administration and continued into the treatment period).

Medications will be categorized into one (and only one) of above classes based on recorded or imputed start and end dates.

Medications will be presented in alphabetical order, by medication category, by Anatomical Therapeutic Classification (ATC) codes and grouped by anatomical main group. Tables will show the overall number and percentage of participants receiving at least one treatment of a particular ATC code and at least one treatment in a particular anatomical main group.

## **Non-drug therapies/procedures**

Records on the concomitant non-drug therapies/procedures eCRF page will be coded using the MedDRA dictionary. All procedures will be classified as prior or concomitant in the same way as done for medications above. Non-drug therapies/procedures in each of these 2 categories will be summarized separately by primary SOC and MedDRA PT.

### **Prior MS medication**

Previous aCD20 therapy (ocrelizumab or rituximab) and reason for discontinuation/switching will be summarized.

### **Injection-related premedication**

Injection related premedication will be identified by subcategory “Injection related premedication” in concomitant medication dataset. Injection related premedication will be summarized separately.

## **2.5 Analysis of the primary objective**

The primary objective of this study is to explore the maintenance of efficacy of ofatumumab in participants with RMS transitioning from aCD20 mAb therapy, as assessed by no change or reduction in the number of gadolinium enhancing (GdE) lesions observed by MRI.

The primary efficacy analysis will be conducted when all participants complete the 12 month on-treatment period or discontinue from the study.

### **2.5.1 Primary endpoint**

The primary efficacy variable is no change or a reduction from baseline in the number of GdE T1 lesions observed by MRI at 12 months of treatment (Yes, No).

### **2.5.2 Statistical hypothesis, model, and method of analysis**

The primary analysis to address the primary objective will be based on the following estimand:

- Treatment of interest: Following a loading dose regimen consisting of once daily doses on days 1, 7 and 14, ofatumumab is given once monthly starting at Month 1. All doses of ofatumumab will be given subcutaneously via an auto injector at a dose of 20mg.
- Population: Relapsing MS participants currently treated with an infused aCD20 mAb, specifically ocrelizumab or rituximab, that have received at least 2 courses of therapy that are switching due to reasons other than safety or efficacy. Further defined through the appropriate inclusion/exclusion criteria to reflect the target population.
- Variable: Reduction or no change from baseline in the number of GdE lesions as observed by MRI (Yes, No).
- Other intercurrent events: Death or treatment/study discontinuation.
- Summary measure: Proportion of participants with no change or a reduction in the number of GdE T1 lesions at Month 12 and corresponding 95% confidence interval.

The 95% CI for the primary endpoint will be calculated using a normal approximation method. In addition, the change from baseline in the number of GdE T1 lesions will also be summarized descriptively by time point and graphically using a longitudinal plot.

Both non-responder imputation (NRI) for missing data and observed data approaches will be applied.

NRI is a conservative imputation method for dichotomous variables. NRI assumes that a participant is a treatment failure, i.e. non-responder, if they do not have a valid month 12 MRI assessment, or if they discontinue the study prematurely and do not have a valid month 12 MRI assessment. Hence, for missing data the primary variable outcome will be imputed to “No”. MRI assessments occurring after the efficacy cut-off will not be included in the analysis.

The primary analysis of the primary efficacy variable will be based on the FAS.

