6.2.3 Recommended treatment of MS Relapse

The decision to treat MS relapses should be based on the Investigator's judgement and/or local clinical practice. If MS relapses require treatment, the standard treatment should consist of a short course of corticosteroids of 3-5 days and up to 1000mg methylprednisolone/day or equivalent on an inpatient or outpatient basis. Standard of care will be followed during treatment as per local clinical practice.

Taper with oral steroids is not permitted. Plasmapheresis may be used only if participant does not respond to standard treatment with corticosteroids.

Investigators should consider the added immunosuppressive effects of corticosteroid therapy and increase vigilance regarding infections during such treatment and in the weeks following administration.

Use of steroids for treatment of MS attack/relapse must be recorded on the Concomitant Medications eCRF. Please refer to restrictions for MRI in [Section 8.3.1](#) concerning the use of steroids and performing the MRI.

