8.3.1 Magnetic Resonance Imaging (MRI)

All participants will undergo MRI scanning of the brain and cervical spine according to the schedules in [Table 8-1](#).

[REDACTED]

MRI scans will be read by the central MRI reading center. Prior to the start of the study, MRI technician from each center will receive an MRI Manual, outlining technical implementation, image quality requirements and MRI administrative procedures.

The site will be asked to program the MRI scanner that is designated for evaluation of the study participants. Site will be asked to perform and submit a dummy scan (so called “dummy or dry run”) to the central MRI reading center to assess the image quality and to evaluate the compatibility of the electronic data carrier. Once the dummy run has been accepted, all the parameter settings for the study specific MRI sequences must remain unchanged for the duration of the study. Finally, if the site is already pre-approved for performing conventional MRI scan sequences by the imaging vendor the dummy or dry run may be skipped.

Each MRI scan performed for the study needs to be previewed by a local neuro radiologist. During the study, the quality of each scan performed will be assessed by the central MRI reading center. The MRI scan should be sent to the central MRI reading center upon completion of each individual scan. As soon as the scan is received by the central MRI reading center, it will be evaluated for quality, completeness and adherence to the protocol. Confirmation of MRI quality or a description of the quality problems, if detected, will be communicated to the site. If a scan is incomplete or incorrectly performed, the study center will be asked to repeat it as soon as possible. After completion of the quality check, all scans will be analyzed according to the MRI protocol.

Restrictions to MRI schedule

To avoid interferences caused by steroids (in regards to Gd⁺-enhancing lesions) for the treatment of MS relapse, the following restrictions apply for this study:

- In case of relapse, if an MRI has been scheduled within 30 days of the initiation of steroid treatment, MRI (with Gd⁺ enhancement) should be performed **before** steroid treatment is initiated.
- No MRI should be performed while a participant is on steroid therapy and within the following 30 days upon termination of steroid treatment.

[figure not shown]

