Because of these restrictions, MRI scheduling can be adjusted accordingly. In case a visit is performed outside the visit window, any subsequent visits should be performed according to the original visit schedule.

Scanning

All sequences/scans will be performed according to the study MRI manual.

MRI scan sequences, such as but not limited to, will include conventional MRI measures of T1 hypointense images (with and without contrast medium, i.e., gadolinium-DTPA), and [REDACTED]

The gadolinium contrast medium may occasionally cause nausea and vomiting. Allergic reactions may also occur very rarely and, in extremely rare instances, can be potentially serious and require immediate anti anaphylactic treatment. Any AE experience due to the contrast medium should be recorded on the AE eCRF.

[REDACTED]

[REDACTED]

[REDACTED]

[REDACTED]

[REDACTED]

[REDACTED]

[REDACTED]

[REDACTED]

[figure not shown]

[REDACTED]

[REDACTED]

[figure not shown]

[figure not shown]
8.3.5 Treatment Satisfaction Questionnaire for Medication TSQM- 9

The Treatment Satisfaction Questionnaire for Medication (TSQM-9) will be used to evaluate the participants' satisfaction with Ofatumumab. The TSQM-9 is a psychometrically sound and valid participant reported outcome to measure participants' satisfaction with medication and a good predictor of adherence across different types of medication and participant population. The TSQM-9 is a 9 item questionnaire having a global satisfaction score ranging from 0-100. The questionnaire consists of 3 domains: satisfaction, convenience and effectiveness (3 items each). The domain scores range from 0 to 100 with higher scores representing higher satisfaction on that domain. ([Bharmal et al. 2009](#))

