#### **2.1.1.8 Efficacy analysis cut-off**

The efficacy analysis cut-off date is 30.4375 days after the date of last study treatment administration.

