**2.4.1 Study treatment / compliance**

**Exposure to study treatment**

Duration of exposure to the study treatment will be calculated as

$$(\text{date of last administration of study drug} - \text{date of first administration of study drug} + 1 + 30.4375 - \sum [(\text{j} + 1)^{\text{th}} \text{ administration date} - \text{j}^{\text{th}} \text{ administration date} - 33.4375]).$$

Where j and j + 1 refer to consecutive study drug administration dates more than 33.4375 days apart (as participants are scheduled to receive the study drug once monthly  $\pm$  3 days).

The duration of exposure will include any periods of temporary dose interruption.

Duration of exposure to the study drug will be summarized by duration category (i.e.,  $\geq 1$  week,  $\geq 2$  weeks,  $\geq 3$  weeks,  $\geq 4$  weeks,  $\geq 8$  weeks,  $\geq 12$  weeks,  $\geq 24$  weeks,  $\geq 36$  weeks, and  $\geq 48$  weeks,  $\geq 52$  weeks).

A listing of the drug doses administered will be provided.

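### The last-dose cut-off can discard an MRI inside the SAP's own Month 12 window and score a participant who completed treatment as a failure

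*SAP*

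**What the plan says.** SAP 2.1.1.8: "The efficacy analysis cut-off date is 30.4375 days after the date of last study treatment administration". SAP 2.5.2 applies this to the primary analysis: "MRI assessments occurring after the efficacy cut-off will not be included in the analysis". Under the same section, anyone in the FAS without a valid Month 12 MRI is a non-responder. Premature discontinuation without such a scan is listed as a second route to the same score, so discontinuation is not needed for a No.

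The estimand in SAP 2.5.2 reads "Other intercurrent events: Death or treatment/study discontinuation", and SAP 2.1.1.11 defines treatment discontinuation as a permanent stop. SAP Table 2-4 accepts a Month 12 MRI on study days 321 to 427, with target day 366. Protocol 12.4 has NRI but no last-dose cut-off, and SAP Table 4-1 lists no changes to protocol analyses.

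The protocol foresees late scans. Section 8.3.1 says "No MRI should be performed while a participant is on steroid therapy and within the following 30 days upon termination of steroid treatment" and "Because of these restrictions, MRI scheduling can be adjusted accordingly". On quality failures it says "If a scan is incomplete or incorrectly performed, the study center will be asked to repeat it as soon as possible".

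On the Month 12 dose, Protocol Table 8-1 marks site administration at Month 12 and Table 8-4 times the Month 12 ECG before dosing, but footnote 22 to Table 8-1 names only Months 1 and 6.

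**The concern.** Two rules govern whether a Month 12 scan counts. Table 2-4 is anchored on the first dose and the cut-off on the last dose, and they can disagree. When they do, an observed scan is discarded and replaced by an imputed failure, although no intercurrent event named in the estimand has occurred. A participant who finished treatment and showed no increase in lesions can then be counted as a failure because of the interval since the last injection. The primary proportion would partly measure scan timing, and the error runs towards understating maintained efficacy.

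A dose hold still open at Month 12 raises a related gap. The documents do not say whether such a hold is an interruption or a discontinuation. If it is not recorded as a discontinuation, the retention endpoint in SAP 2.7.2 counts the participant as retained, while the primary analysis can count the same person as a failure despite an observed scan.

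**Working it through.** **Inputs.** Cut-off: last dose day + 30.4375 (SAP 2.1.1.8). Scan window: days 321 to 427, which is 107 days (SAP Table 2-4). Scheduled days: Month 11 = 336, Month 12 = 366 (SAP Table 2-1). Dose and visit tolerance: ±3 days (Protocol 6.7.2 and 8). Relapse steroids: "short course of corticosteroids of 3-5 days" (Protocol 6.2.3). Planned n = 100 (SAP 3).

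**1. The plan's own precision.** Half-width = 1.96 × √(p(1−p)/100). For p = 75%, 80% and 85% this gives 8.49, 7.84 and 7.00 points, matching the stated 8.5%, 7.8% and 7.0%.

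**2. Month 12 dose given on day 366.** Cut-off = 366 + 30.4375 = 396.4. Scans on days 397 to 427 are dropped: 31 of the 107 window days. If the dose is on day 363 the cut-off is 393.4; if on day 369 it is 399.4.

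**3. On-schedule scans.** With dose and scan each on days 363 to 369 there are 7 × 7 = 49 combinations. The scan is at most 6 days after the dose, so 0 of 49 are lost.

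**4. How a scan reaches day 397.** One route is a late repeat of a failed scan. The other is steroid deferral. A course of L days starting on day s ends on day s + L − 1, so the first permitted scan is day s + L − 1 + 31.
- L = 5, s = 362 to 369: first scan on days 397 to 404.
- L = 3, s = 364 to 369: first scan on days 397 to 402.

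All exceed 396.4 and lie inside the window. Each case requires that the scan was not done before steroids, although Protocol 8.3.1 asks for that when an MRI is scheduled within 30 days of starting them. Every start day listed is within 7 days of a Month 12 scan on days 363 to 369, so the instruction applies each time.

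**5. If Month 11 (day 336) were the last dose.** Cut-off = 366.4. Scans on days 367, 368 and 369 would be lost although they are within the protocol's ±3 days.

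**6. Effect on the estimate.** Each responder rescored as No lowers the proportion by 1/100 = 1 point. The documents do not give the number affected. As an assumed range from a true 85%: 1 affected gives 84% (half-width 7.2), 3 give 82% (7.5) and 5 give 80% (7.8).

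**The case against.** **The supplementary analysis covers it.** SAP 2.5.4.1 repeats the analysis with post-cut-off scans, under both NRI and observed data. This will show the effect, but the primary estimate stays as it is. It also restores every post-cut-off scan, including those after discontinuation, so it does not isolate participants who completed treatment. The observed-data analysis in 2.5.4 keeps the cut-off.

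**The cut-off keeps the endpoint on treatment.** This is a sound reason for applying it to participants who stopped. It does not explain scoring someone who completed treatment as a failure when the estimand names no event that they had.

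**The steroid route departs from the protocol, and few will be affected.** Both points stand. There is also no hypothesis test, and the SAP itself describes NRI as conservative. These limit the size of the point but do not remove it.

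A reader might infer three stronger claims that the documents do not support:
- *That the cut-off contradicts the exposure formula.* SAP 2.4.1 uses 33.4375 days for "consecutive study drug administration dates more than 33.4375 days apart". That is a tolerance between doses. The tail after the last dose is 30.4375 days in that formula and in the on-treatment period of SAP 2.1.1.6, so the cut-off agrees with both.
- *That ordinary on-schedule scans are lost.* This needs Month 11 to be the last dose. Only on that reading would 21 of 49 compliant day combinations fall after the cut-off. Tables 8-1 and 8-4 point the other way, and footnote 22 concerns which doses staff observe.
- *That every in-window scan during an open dose hold should count in the primary analysis.* With a last dose on day 305 (Month 10), that would admit scans up to 427 − 305 = 122 days later. This is a trade-off and not a correction. An unlifted hold at Month 12 might also reasonably be read as a permanent stop. What is missing is the classification.

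**Conclusion.** The point holds in a limited form. The SAP can discard an observed MRI inside its own Month 12 window and score a participant who completed treatment as a failure, with no intercurrent event from the estimand. With a Month 12 dose on day 366, only scans on days 397 to 427 are exposed. The number is unknown and probably small, at 1 percentage point per affected responder at n=100, against planned half-widths of 7.0 to 8.5 points.

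Two assumptions matter. First, a scan that is not included is taken as not valid; the SAP leaves valid undefined, but 2.5.4.1 adds these scans back and still applies NRI, which makes this the natural reading. Second, a Month 12 dose is taken as given; if it is not, compliant scans on days 367 to 369 are at risk too. It should be fixed because the rule conflicts with the estimand and the remedy is simple, not because a large bias is shown.

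**What to change.** 1. In the primary analysis, accept any valid MRI in the Table 2-4 Month 12 window for participants who completed the treatment period and are not recorded as permanently discontinued. Apply the last-dose cut-off only to recorded discontinuers, and define valid.
2. State before database lock whether a dose hold still open at Month 12 counts as discontinuation for analysis. Use the same classification for the primary and retention endpoints.
3. Keep the present cut-off version as a sensitivity analysis, and report how many scans fall after the cut-off.
4. Reconcile Protocol Table 8-1, its footnote 22 and Table 8-4 on the Month 12 dose.

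**Cost.** Items 1 to 3 are SAP text and programming on scans already collected. Item 4 needs a protocol clarification. The downside is that some accepted scans may be up to 427 − 366 = 61 days after a day 366 last dose; the retained cut-off version shows how much that matters.

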### **2.5.3 Handling of missing values/censoring/discontinuations**

For participants with missing number of GdE T1 lesions at Month 6 and Month 12, NRI method will be used.

### **2.5.4 Sensitivity analyses**

The primary analysis will be repeated to analyze no change or a reduction from baseline in the number of GdE T1 lesions observed by MRI at 12 months of treatment (Yes, No), based on observed data. MRI assessments occurring after the efficacy cut-off will not be included in the analysis.

#### **2.5.4.1 Supplementary analysis:**

The primary analysis will be repeated to analyze no change or a reduction from baseline in the number of GdE T1 lesions observed by MRI at 12 months of treatment (Yes, No), including any assessments after the efficacy analysis cut-off. Both NRI for missing data and observed data approaches will be applied.

## **2.6 Analysis of the key secondary objective**

There is no key secondary objective for this study.

## **2.7 Analysis of secondary objective**

Refer to [Table 1-1](#) of [Section 1.2](#) for the list of secondary objectives.

The secondary efficacy analysis will be conducted after all participants complete the 12 month on-treatment period or discontinue from the study.

### **2.7.1 Secondary endpoints**

The secondary endpoints are as follows:

1. Retention on study treatment from baseline to Month 6, and to Month 12 (Yes, No)

2. Change from baseline in lymphocytes, including total CD19+ B cell counts and CD20+CD3+ T cell counts, obtained by fluorescence activated cell sorting (FACS) at Months 6 and 12
3. The Columbia Suicide Severity Rating Scale (C-SSRS) at Months 6 and 12
4. Treatment Satisfaction Questionnaire for Medication (TSQM-9) scores (including domains) at baseline vs Month 6 and vs Month 12
5. Treatment-emergent adverse events (TEAEs)

## **2.7.2 Statistical hypothesis, model, and method of analysis**

The following statistical analyses are planned for the secondary endpoints:

1. Retention on study treatment from baseline to Month 6, and to Month 12 (Yes, No) will be summarized using frequency counts and percentages for the FAS. Retention will be based on the number of study drug discontinuations.
2. Biomarker analysis – See [Section 2.12.1](#)
3. C-SSRS analysis – See [Section 2.8.3.1](#)
4. TSQM-9 analysis – See [Section 2.11.1](#)
5. TEAEs analysis – See [Section 2.8.1](#)

## **2.8 Safety analyses**

Unless stated otherwise, all safety analyses will be summarized for the SAF. Only data captured prior to the safety cut-off will be used for safety analyses.

### **2.8.1 Adverse events (AEs)**

An adverse event (AE) is any untoward medical occurrence (i.e., any unfavorable and unintended sign [including abnormal laboratory findings], symptom or disease) in a participant or clinical investigation of a participant after providing written informed consent for participation in the study. That means that a participant can report AEs before having started study medication. For reporting purposes, the main focus will be on treatment emergent adverse event (TEAE), defined as any adverse event which started on or after the day of first dose of study drug, or before 30 days after treatment end date, if severity at baseline if missing or if post baseline severity is greater than baseline severity.

The number (and percentage) of participants with TEAEs will be summarized in the following ways:

- by primary SOC and PT
- by primary SOC, PT and maximum severity

Separate summaries will be provided for:

- study drug related TEAEs
- serious adverse events (SAEs)
- TEAEs leading to permanent study drug discontinuation
- TEAEs leading to study drug interruption

The MedDRA version used for reporting the study will be described in a footnote. Missing CTCAE grades will not be imputed. If a participant reported more than one AE with the same PT, the AE with the greatest severity will be presented. A participant with multiple AEs within a primary SOC is only counted once towards the total of the primary SOC.

All AEs will be listed.

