12.5.2 Safety endpoints

For all safety analyses, the safety set will be used. All listings and tables will be presented by treatment. Unless explicitly otherwise stated, only data up to and until B cells are repleted after the final study drug administration for study completers or until the participant initiates a commercial MS disease modifying therapy or until the end of Safety Follow-up for premature withdrawals will be included in the analysis and data beyond this time point for a participant will be excluded from safety analysis. In addition, a separate summary for death including on treatment and post treatment deaths will be provided. In particular, summary tables for adverse events (AEs) will summarize only on-treatment events, which started or worsened during the on-treatment period (treatment-emergent AEs).

The on-treatment period for safety analysis lasts from the date of first administration of study drug until B cells are repleted after the date of the last actual administration of study drug for study completers or until the participant initiates a commercial MS disease modifying therapy or until the end of Safety Follow-up.

Adverse events

All information obtained on adverse events will be displayed by treatment and participant. The number and percentage of participants with AEs of special interest/related to identified and potential risks will be summarized in the following ways:

[figure not shown]
- By treatment, primary system organ class and preferred term.
- By treatment, primary system organ class, preferred term and maximum severity.
- By treatment, pre-defined topic of interest, primary system organ class and preferred term.

Separate summaries will be provided for study medication related adverse events, serious adverse events, and other significant adverse events leading to discontinuation.

The number and percentage of participants with adverse events of special interest will be summarized by treatment, primary system organ class and preferred term. A participant with multiple AEs within a category is only counted once towards the total of that category.

Vital signs

All vital signs data may be listed by participant, and visit. Abnormalities will be flagged. Descriptive statistics for change from baseline will be provided by visit.

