#### **2.1.1.5 Screening, baseline and post-baseline definitions**

**Screening** refers to any procedures (e.g., checking inclusion and exclusion criteria) performed prior to the date of the first dose of study treatment. Per protocol, participant informed consent must be obtained prior to performing any study related activity. The date of signing of informed consent is the start date of the screening period. Any assessment obtained during the screening period will be labelled screening assessment.

**Baseline** is the last assessment (including unscheduled visits) obtained before the first administration of the study treatment. No visit windows will be needed for the identification of baseline assessment. All assessments obtained after the first administration of study treatment are considered as **post-baseline** unless otherwise specified.

For blood pressure **vital sign values**, the baseline is the average of the non-missing values of the 3 measurements taken on the last visit prior to the first administration of study drug.

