### **2.1.1.9 Safety analysis cut-off**

The safety analysis cut-off is the same as the efficacy analysis cut-off. The safety analysis cut-off is 30 days after the treatment end date but for programming purposes 30.4375 days will be used.

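### The TEAE definition in SAP 2.8.1 joins its date limits with *or*, so adverse events that resolved before the first dose can be counted as treatment-emergent

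*SAP*

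**What the plan says.** SAP 2.8.1 defines a TEAE as "any adverse event which started on or after the day of first dose of study drug, or before 30 days after treatment end date", and continues "if severity at baseline if missing or if post baseline severity is greater than baseline severity". Just before this, it notes that events are collected from consent: "That means that a participant can report AEs before having started study medication".

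Three other SAP rules bear on the definition:
- Section 2.8 sets an upper limit: "Only data captured prior to the safety cut-off will be used for safety analyses".
- Section 2.1.1.9 places that limit: "The safety analysis cut-off is 30 days after the treatment end date but for programming purposes 30.4375 days will be used".
- Section 2.1.1.5 says that baseline "is the last assessment (including unscheduled visits) obtained before the first administration of the study treatment". It has no rule specific to the severity of adverse events.

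Protocol 12.5.2 says that the adverse event tables cover "only on-treatment events, which started or worsened during the on-treatment period (treatment-emergent AEs", and it starts the on-treatment period at the first administration of study drug. SAP Table 4-1 lists no change from the protocol's analyses. TEAEs are a secondary endpoint in both documents.

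**The concern.** A TEAE definition needs an earliest and a latest date, and both must hold. With *or* between them, neither date excludes anything, so the whole job of keeping out pre-dose events falls to the severity clause. That clause is itself garbled, and it depends on a baseline severity that the SAP does not define for an event already over by Day 1.

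Pre-dose events are to be expected. Screening lasts up to 28 days, adverse events are recorded from consent, and the screening visit includes a gadolinium MRI. Protocol 8.3.1 mentions nausea and vomiting from the contrast and instructs: "Any AE experience due to the contrast medium should be recorded on the AE eCRF".

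At stake are the TEAE tables by system organ class, preferred term and maximum severity, and the registry table of non-serious TEAEs with incidence above 5%. In a single-arm study these percentages are read directly as the safety profile of ofatumumab.

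**Working it through.** **Step 1. The date condition.** Let S be the start of the event, F the first dose and E the end of treatment. The SAP requires S ≥ F *or* S < E + 30. If S ≥ F, the first part holds. If S < F, then S < F ≤ E < E + 30, so the second part holds. Every date qualifies.

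**Step 2. The severity condition.** Apply the clause to the whole sentence. An event that is new on treatment has no pre-dose grade, so it qualifies because its baseline severity is missing. An event that resolved in screening is equally absent at first dose. If absence means missing for the first event, it means missing for the second, and both pass. If instead the screening grade is carried as the baseline severity, the resolved event has nothing worse after baseline and fails. The SAP does not choose between these. It does say that missing CTCAE grades are not imputed, so an ungraded screening event passes either way.

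**Step 3. Six kinds of event against the definition.** The two right-hand columns combine the date and severity conditions.

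| Event | Severity clause | SAP text (*or*) | Bare swap to *and* |
|---|---|---|---|
| Began and ended in screening, its grade taken as baseline | fails | not a TEAE | not a TEAE |
| Began and ended in screening, baseline severity treated as missing | passes | **TEAE** | not a TEAE |
| Began in screening, ongoing, not worse | fails | not a TEAE | not a TEAE |
| Began in screening, worsened on treatment | passes | TEAE | **lost** |
| New on treatment | passes | TEAE | TEAE |
| New 60 days after last dose | passes | passes, then removed by the SAP 2.8 cut-off | not a TEAE |

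The second row is the error. The fourth row shows why replacing the one word is not enough: Protocol 12.5.2 counts events that worsen on treatment.

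**Step 4. Another way to parse the sentence.** If the severity clause attaches only to the second date limit, a new on-treatment event qualifies on the first limit alone. The resolved screening event still reaches the second limit and still passes if its baseline severity is missing.

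**Step 5. Other rules.** The cut-off in SAP 2.8 and 2.1.1.9 acts only at the late end. No rule in SAP 2.8 or 2.8.1 removes an event because it started before the first dose.

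**Step 6. Possible size.** The documents state no figure to reproduce and give no screening event rate, so this is an illustration. Assume a constant rate λ per participant-year in screening and on treatment, a participant who completes treatment, and that every event in the 28 screening days is let in. With the last dose on study day L (336 or 366, the Month 11 and Month 12 days in SAP Table 2-1), the window is t = L + 30 days. The share with any TEAE is 1 − exp(−λt/365.25), and with leakage t becomes t + 28. For λ = 1 and L = 336: 1 − exp(−366/365.25) = 63.3%, and 1 − exp(−394/365.25) = 66.0%, a rise of 2.7 points.

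| λ per year | L = 336 | L = 366 |
|---|---|---|
| 0.1 | 9.5% to 10.2% (+0.7) | 10.3% to 11.0% (+0.7) |
| 0.5 | 39.4% to 41.7% (+2.3) | 41.8% to 44.0% (+2.2) |
| 1 | 63.3% to 66.0% (+2.7) | 66.2% to 68.7% (+2.5) |
| 2 | 86.5% to 88.4% (+1.9) | 88.6% to 90.2% (+1.6) |
| 3 | 95.1% to 96.1% (+1.0) | 96.1% to 96.9% (+0.8) |

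Screening makes up 28/394 = 7.1% or 28/424 = 6.6% of the enlarged window.

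A single preferred term can be more sensitive. With 100 participants, an incidence above 5% means at least 6, so one misclassified participant moves a term with 5 true cases into the registry table.

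**The case against.** The best defence is that the intent can be recovered. The SAP says that it implements Protocol Section 12 and declares no changes, and Protocol 12.5.2 is clear that events must start or worsen on treatment. The date-imputation rules in SAP 5.1.2 separate events that ended before treatment start and give them their own reference date, a step with little purpose if those events were meant to be TEAEs. A programmer who carries the screening grade as baseline severity would exclude graded resolved events despite the *or*. All of this stands as evidence of intent. It does not change the operative sentence, and the SAP is what gets programmed.

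The defence also limits the point, because the documents do not support several stronger readings that a reader might infer:
- *Every resolved screening event counts automatically.* It does not. The event must also pass the severity clause, and for a graded event that depends on a rule the SAP leaves unstated.
- *The tables of TEAEs leading to discontinuation or interruption are distorted.* An event that was over before the first dose cannot have led to stopping or interrupting the drug.
- *Without a control arm the misclassification cannot be seen.* All adverse events are listed, and SAP 2.1.1.3 gives pre-dose dates a negative study day, so a reader of the listing can find them. The summary tables would not show them.
- *A definite number of participants is affected.* A guess such as 3 to 10 in 100 has no basis in the documents. For contrast reactions in particular, the MRI is repeated at Months 6 and 12, so the same terms will also include true on-treatment events.

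**Conclusion.** The definition is wrong as written. Its date condition has no lower limit, and the severity clause restores one only under a rule for baseline severity that the SAP does not state. Resolved pre-dose events can therefore be counted as TEAEs, against Protocol 12.5.2. That they will be counted is not shown.

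The size is unknown. For the percentage with any TEAE it is probably small: a rise of 0.7 to 2.7 points under the assumed constant rates of 0.1 to 3 per participant-year with all screening events let in. That range rests on treatment to Month 11 or 12 and would not carry over to participants who stop early. It does not measure the effect on single preferred terms. Confidence in the drafting fault is high; confidence in its numerical effect is not.

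**What to change.** Replace the sentence in SAP 2.8.1 with a definition in two limbs. A TEAE is an adverse event that either:

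(a) started on or after the date of first dose *and* no later than the SAP safety cut-off (30 days after treatment end, programmed as 30.4375 days); or

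(b) started before the first dose and increased in severity on or after the first dose and no later than that cut-off.

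Events that started and ended before the first dose are listed but not tabulated as TEAEs. State also which pre-dose grade serves as baseline in limb (b), and what happens when that grade is missing. Do not merely change *or* to *and*, because that drops the events in limb (b).

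Name the cut-off in the text rather than the on-treatment period: SAP 2.1.1.6 defines that period for efficacy only, and Protocol 12.5.2 defines it differently for safety. The end of the window is a separate matter. Protocol 12.5.2 runs to B-cell repletion, a commercial MS therapy or the end of Safety Follow-up, whereas SAP 2.1.1.9 stops at 30 days, and the two passages must be reconciled.

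The cost is a short replacement text in the SAP, a check of the program that sets the TEAE flag and, if the flag changes, a rerun of the adverse event tables. No new data are needed.
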